1.17 OUTCOMES

1.17.1 Primary Effectiveness Outcome

Survival time from cardiovascular hospitalisation all-cause mortality: defined in whole days measured as time from randomisation until date of first cardiovascular hospital or death from any cause, whichever happens first. Participants who withdraw or are lost to follow-up will be censored at the date last known to be alive and free from cardiovascular hospitalisation. Participants not having an event at the time of the analysis will be censored at the last date known to be alive and free from cardiovascular hospitalisation.

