1.20 FOLLOW-UP

Patients will be followed up during their index hospital stay (or stays for planned staged PCI). Primary and secondary outcome measurements will be collected for a minimum follow-up of 4 years and given a 41-month recruitment period will result in a median follow-up length of 5.3 years. Outcome measurements during follow-up (excluding PROMS and 30-day SAEs) will be determined through routinely collected HES/ONS data.

Quality of Life Assessments, and Health Economic Outcomes will be ascertained at baseline, and then using telephone follow-up or self-completion using the ResearchApp™ (Healthbit®) at 3 months, 6 months, 12 months and then annually post randomisation (\pm 28 days) until the end of trial follow-up. Please refer to **Table 1** for further details about follow up visits.

Consent for life-long trial follow-up following completion of this trial's current funded period (i.e., beyond 41 months recruitment + 48 months follow-up period) using routinely collected healthcare data will be obtained.

Consent will be sought for relatives/friends to provide information if and when it is established that the participant is not contactable, has lost capacity or is too unwell, to ascertain what has happened to them. Where available and willing, two alternate contacts should be sought, through the means of the Consent to Contact Form. If it is subsequently determined that the participant has lost capacity or has become too unwell to respond to follow-ups, the research teams will initially attempt contact with the named relative(s)/friend(s) to seek consent using the Personal Consultee Information Sheet, which they may be provided with in advance, and Personal Consultee Declaration form, which can only be signed in the event that the participant has lost capacity. We will also seek consent to notify their general practitioner (GP) of their participation of their participation in the trial.

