6. Where patients have one or more chronic total occlusions supplying viable myocardium, the participant should only be enrolled if the necessary expertise in CTO-PCI is available, if the Heart Team consider the risk/benefit balance favours CTO intervention.

7. Staging PCI is permitted where the cardiologist feels that this is in the patient's best interest, but the intention to stage must be documented at the first procedure.
8. Mechanical circulatory support should be reserved for bailout in case of mechanical complication of the PCI or developing cardiogenic shock, unless new evidence arises during the course of the trial to indicate benefit to routine use.

Details of physiological, intracoronary imaging, and advanced percutaneous methods will be recorded in the CRF as will mechanical circulatory support.

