1.27.5 Duration of the Intervention

Revascularisation will be completed as per institutional norms after consideration of presentation, access to care, and resources. In ACS, revascularisation should be encouraged to be undertaken during the index admission but patients may be discharged to return for PCI or CABG. If this is the case, revascularisation should be undertaken as soon as dictated by clinical urgency but no more than 6 weeks (+/- 28 days) of randomisation. For non-ACS cases, the assigned treatment should be undertaken as soon as possible after randomisation and no more than 18 weeks (+/- 28 days) later.

Table 1 Schedule of Processes

Assessment	Screening	Baseline Assessment	Index Procedure	Post Procedure until Discharge	3 Months	6 Months ¹	12 Months ¹	6 Months and every 6 Months to 4 Years	Every 12 months to 4 Years ¹	Following LPLV
	-90 to 0	-30 to 0	Day 0	Day of revascularisation procedure until hospital discharge	+/- 28 days after Day 0	+/- 28 days after Day 0	+/- 28 days after Day 0	6 months +/- 28 days after Day 0	+/- 28 days after Day 0	
Informed Consent	X									
Inclusion/Exclusion	X									
Revascularisation and feasibility confirmed by local Heart Team	X									
Pregnancy Test ²	X ²									
Demographics, Height and Weight		X								
Medical/Cardiac History (including long term conditions and severity of cardiac diseases)		X								
Risk Scores (BCIS Myocardial Jeopardy Score and EuroSCORE II)		X		X						
Randomisation		X								
NYHA Class and CCS Class		X		X	X			X		
Kansas City Cardiomyopathy Questionnaire (KCCQ)		X		X	X			X		

Assessment	Screening	Baseline Assessment	Index Procedure	Post Procedure until Discharge	3 Months	6 Months ¹	12 Months ¹	6 Months and every 6 Months to 4 Years	Every 12 months to 4 Years ¹	Following LPLV
	Visit window (days) (± number of days this visit can take place ahead or after its due date)	-90 to 0	-30 to 0	Day 0	Day of revascularisation procedure until hospital discharge	+/- 28 days after Day 0	+/- 28 days after Day 0	+/- 28 days after Day 0	6 months +/- 28 days after Day 0	+/- 28 days after Day 0
Seattle Angina Questionnaire 7 (SAQ-7)		X		X	X			X		
EQ-5D-5L		X ¹			X ¹	X ¹	X ¹		X ¹	
Health Care Resource Use		X ¹			X ¹	X ¹	X ¹		X ¹	
Revascularisation procedures and revascularisation completeness			X							
Procedural Data Collection				X						
Concomitant Medications ³		X ³	X ³	X ³	X ³			X ³		
Clinical Events ⁴			XXXXXXXXXXXXXXXXX ⁴							

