1.31 OUTCOMES POST RANDOMISATION

Trained staff will use the Investigator portal in the ResearchApp™ (Healthbit®) to collect the following:

1. Baseline data will include patient demographics, such as age, sex, and ethnicity, as well as long term conditions and pre-operative investigations, severity of cardiac disease, risk scores (BCIS Jeopardy Scores. EuroSCORE II), revascularisation procedures, completeness of revascularisation, defined as change in BCIS-JS from baseline.
2. Mortality will be ascertained in UK participants through ONS data access request.
3. Outcomes until hospital discharge:
 - a) Unplanned mechanical circulatory support defined as the need for IABP, ventricular assist device or ECMO postoperatively.
 - b) New onset renal failure requiring renal replacement therapy (excluding dialysis during cardiopulmonary bypass (CPB)).
 - c) New focal neurological deficit (stroke) lasting more than 24 hours confirmed by clinical assessment and brain imaging.
 - d) Infection: defined as septic shock with positive blood cultures; pneumonia defined as autopsy diagnosis or roentgenographic infiltrate and at least two of the following three criteria: fever, leukocytosis, and positive septum culture; and/or deep sternal or leg wound infection requiring intravenous antibiotics and/or surgical debridement.
 - e) Bleeding requiring surgical or percutaneous intervention.
 - f) Length of stay in the Intensive Care Unit (ICU) readmissions and hospital (time to discharge from acute care after index hospitalisation; this includes time to discharge from satellite acute care units) and Days Alive and Out of Hospital at 6 months.
4. Clinical effectiveness and adverse outcomes post discharge will be ascertained using HES data obtained from NHS Digital using Primary Diagnostic International Classification of Diseases, Tenth Revision (ICD10) codes as previously described (8). ONS data will be used for ascertainment of mortality. NHS numbers will be used to submit ONS/NHS Digital data access requests by the LCTU after last participant/last visit in the UK arm.

For the primary outcome, the following HES codes will be used:

- a) All-cause mortality (ICD10): (dismeth = 4) OR (a linked record in ONS death registry). Follow-up begins the day after operation date.

- b) Cardiovascular hospitalisation and hospitalisation admission after the index admission with ICD10: I00 to I99 (which encompass all the cardiovascular diagnoses) as the *primary* diagnostic code.

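### The primary-outcome HES rule depends on an undefined index admission and excludes no planned admissions, so planned PCI stages and planned returns for the assigned procedure could be counted as primary events

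*Protocol*

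**What the plan says.** Section 1.17.1 defines the primary outcome as "measured as time from randomisation until date of first cardiovascular hospital or death from any cause, whichever happens first". Section 1.46 uses the same origin. Neither says which cardiovascular admissions qualify.

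Section 1.31 item 4 turns this into an extraction rule. Item 4(b) reads "Cardiovascular hospitalisation and hospitalisation admission after the index admission with ICD10: I00 to I99 (which encompass all the cardiovascular diagnoses", and the rest of the sentence requires the code to be the primary diagnosis. Item 4(a), on mortality, adds "Follow-up begins the day after operation date".

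The reference point in 4(b) has no definition, and related terms point in different directions:

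- Section 1.27.5, on acute coronary syndrome (ACS): "revascularisation should be encouraged to be undertaken during the index admission but patients may be discharged to return for PCI or CABG". Here the index admission is the presenting stay, and the assigned procedure may fall in a later one.
- Section 1.20: "Patients will be followed up during their index hospital stay (or stays for planned staged PCI". Here there can be several index stays, staged ones included.
- Section 1.31 item 3(f) speaks of the index hospitalisation next to intensive-care stay, which suggests the procedure stay.

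Section 1.27.2 item 7 says "Staging PCI is permitted where the cardiologist feels" it serves the patient, and adds that "the intention to stage must be documented at the first procedure". Section 1.27.3 (CABG) has no counterpart. Section 1.32 plans no outcome adjudication. Section 1.17.2 item 6 sets the assigned treatment aside for the secondary revascularisation outcome; the primary outcome has no such clause.

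**The concern.** The rule selects on diagnosis and order of admission, not on whether the admission was planned. A second PCI stage in its own admission would ordinarily carry a coronary primary code, which lies within I00 to I99. Read literally, it follows the index admission and is a first primary event. Only the PCI arm can produce such events, so they would push the hazard ratio towards CABG.

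A patient with ACS who is discharged and returns for the assigned procedure raises the same question in either arm. On the Section 1.27.5 usage the return falls after the index admission and counts; on the item 4(a) clock it does not.

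Nothing later in the protocol would catch this. There is no adjudication, HES data are requested only after the last visit, and the per-protocol population in Section 1.43 keeps patients who were staged as planned, because they were treated as randomised.

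**Working it through.** **1. The plan's own figures.** Inputs from Section 1.16: HR 0.7, 1:1 allocation, 90% power, two-sided alpha 0.05, 70% event frequency at 5 years on PCI, crossover 8% (range 7-9%), 630 patients. From Section 1.20: 41 months' accrual and a 4-year minimum follow-up.

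Schoenfeld: D = 4(1.960 + 1.282)² / (ln HR)².

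- HR 0.70, no crossover: 331 events.
- 8% CABG-to-PCI crossover: HR = 0.92 × 0.7 + 0.08 = 0.724, giving 403 (Freedman: 410).
- 9% crossover: HR = 0.91 × 0.7 + 0.09 = 0.727, giving 414.

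Expected events: λ = −ln(0.3)/5 = 0.241 per year on PCI and 0.7λ on CABG. With uniform accrual over A = 41/12 years and F = 4, the event fraction is 1 − [exp(−λF) − exp(−λ(F+A))]/(λA), which is 0.740 on PCI and 0.613 on CABG. Then 315 × (0.740 + 0.613) ≈ 426. The stated 414 events and 630 patients are sound and are not in dispute. The question is which admissions are events.

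**2. If planned PCI stages are counted.** Assumptions, because the protocol gives no figures: a fraction q of PCI patients has a separate staged admission, uniformly 4 to 12 weeks after randomisation, and all of these count. Exponential times as above, 315 per arm, no crossover, 2,000 simulated trials per row. CABG is called falsely favoured when the two-sided 5% log-rank test of Section 1.46 rejects in its direction.

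| q | HR read when true HR is 1.0 | CABG falsely favoured | HR read when true HR is 0.70 |
|---|---|---|---|
| 0 | 1.00 | about 3% (nominal 2.5%) | 0.70 |
| 5% | 0.94 | 9.5% | 0.66 |
| 10% | 0.88 | 29% | 0.62 |
| 20% | 0.77 | 84% | 0.55 |
| 30% | 0.67 | 99% | 0.48 |

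A separate run at 5%, 10% and 20% gave 0.94, 0.88 and 0.76, with 11%, 30% and 83%. The differences are simulation noise.

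Hand check at q = 10%, true HR 1.0: 0.10 × 315 = 31.5 early PCI events, each adding about −0.5 to the log-rank score, so U ≈ −15.75. With about 474 events, V ≈ 474/4 = 118.5. Then HR ≈ exp(−15.75/118.5) = 0.88, z ≈ −15.75/√118.5 = −1.45, and P(Z < −1.96 + 1.45) ≈ 30%. This agrees.

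**3. If planned returns for the assigned procedure are counted.** Assumed 1 to 6 weeks after randomisation, no staging.

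| Returns, PCI / CABG | HR read when true HR is 1.0 | HR read when true HR is 0.70 |
|---|---|---|
| 20% / 20% | 1.00 | 0.77 (power 95% falls to 81%) |
| 40% / 40% | 1.00 | 0.83 (power 55%) |
| 20% / 40% | 1.34 | 1.09 |
| 40% / 20% | 0.75 | 0.59 |

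Equal returns leave the error rate at about 5% and dilute the effect. Unequal returns bias in whichever direction they differ. The 95% starting power exceeds the planned 90% because these runs contain no crossover.

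**The case against.** The strongest reply is that the protocol already treats planned stages as part of the index treatment. Section 1.20 names several index stays for staged PCI, Section 1.27 scores completeness after the final stage, and Section 1.33 refers to the first index PCI procedure. On that reading 4(b) does not count a planned stage. Likewise, the item 4(a) clock would put the operative stay before follow-up, and for elective patients recruited from clinic the procedure stay is the only natural index admission. Section 1.31 also relies on a published coding method and leaves HES codes for the pre-specified outcomes to the SAP; neither is to hand.

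Much of this stands. A reader might infer that planned stages will be scored as failures and a CABG benefit manufactured. The documents do not support that as settled: Section 1.20 allows the opposite reading, and staging is permitted, not required. Nor do they show that returns differ between arms, since both arms may be deferred and no proportions are given.

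It does not dispose of the point. Section 1.20 is about follow-up during the hospital stay and does not amend 4(b). The item 4(a) clock conflicts with the randomisation origin in Sections 1.17.1 and 1.46. The primary-outcome rule is already written into the protocol, so this is more than detail left to the SAP. A programmer applying it to HES would have to choose a reading.

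**Conclusion.** The concern holds as an ambiguity in the primary-event rule, one available reading of which would seriously distort the primary test. Index admission is undefined and used inconsistently, two time origins are stated, and no planned admission is excluded.

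If planned stages were counted, a true HR of 1.0 would read about 0.94, 0.88 or 0.76 at 5%, 10% or 20% staged, with CABG falsely favoured in about 10%, 30% or 83% of trials. These figures show how sensitive the result is; they do not predict this trial. They rest on assumed staging proportions and timing, on every such stage being a separate admission with an I00 to I99 primary code, and on the Section 1.46 test alone. Section 1.10 also asks for an HR of 0.7 or below, which would make a declared success rarer but would not remove the shift in the estimate. For returns, the size and direction of any bias are unknown.

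Because the primary conclusion can turn on the reading chosen, it should be settled before outcome data are extracted.

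**What to change.** - Define index admission once and reconcile Sections 1.17.1, 1.20, 1.27.5 and 1.31 with it. Keep randomisation as the single time origin and correct item 4(a) accordingly.
- State in 4(b) that two kinds of admission are not primary events: the planned admission for the first trial revascularisation, whichever procedure is performed, so that the expected 8% of crossovers are treated alike; and PCI stages documented as intended at the first procedure. Identify both by matching HES spells to eCRF procedure dates.
- State that an unplanned (emergency) cardiovascular admission after randomisation and after the presenting stay counts even if revascularisation is then done during it. Without this, the exclusion and the event rule overlap for a deferred patient who is readmitted urgently.
- Confirm that the eCRF captures the intention to stage. Section 1.27.2 requires it to be documented, but its list of CRF items does not name it.

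The cost is protocol and SAP wording and one linkage step. Sample size and follow-up do not change.

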1.32 OUTCOME ADJUDICATION

Given the pragmatic and objective nature of this trial, coding accuracy (>96%) (30) of the primary outcome, and given the limited added value of adjudication beyond high quality prospectively, independently coded events (31), no outcome adjudication is planned for the trial.

RECORDING AND REPORTING SAEs

BCIS-4 is not a clinical trial of an investigational medicinal product (CTIMP) therefore the usual monitoring of pharmacovigilance and associated terminology is not relevant. Furthermore, the trial is a comparison of two accepted management pathways which involve routine clinical care; neither intervention is a research procedure. The complications of both PCI and CABG are well known and dependent on the age and existing comorbidities of the patient. All of the participants in the trial will, in the opinion of the multidisciplinary Heart Team, be eligible for both treatments. Trial participants are also typically younger and fitter than the overall target population and therefore at lower risk for adverse events. For example, **Figure 3** shows freedom from death or cardiovascular hospitalisation in people with HF following PCI or CABG in the general English population (the target population) and also in the population matched to individual participant data from the STICH trial of CABG versus no treatment in iLVSD. The data demonstrates that the typical trial population is at lower risk of death or cardiovascular hospitalisation, particularly in the long term.

1.33 EXPECTED SERIOUS ADVERSE EVENTS

The risk of intervention is not negligible. In the STICH trial, participants with ischaemic left ventricular dysfunction undergoing CABG had 5% mortality at 30 days post-surgery. In contrast, the peri-procedural risk of death following PCI should be less, although the overall burden of SAEs may be similar. In the SYNTAX trial (22) for example, the rate of Major Adverse Events at 30 days was the same in both CABG and PCI groups (only 7% of participant in this trial had iLVSD). However, with time, recurrent symptoms and repeat revascularisation are typically higher in the PCI treated patients, meaning that freedom from death or revascularisation is lower. This is evident in the Kaplan Meier curves in Figure 3, where the CABG curve (blue) is initially lower, but then crosses the PCI curve (red) after 3-6 months.

[figure not shown]

Figure 3 Freedom from death or cardiovascular hospitalisation in people with heart failure undergoing CABG or complex PCI in England 2013-2018, or matched to the STICH cohort (8)

However, other trials have identified important differences in early expected adverse events following both PCI or CABG (32). These include the risk of stroke, severe acute kidney injury (AKI), unplanned mechanical circulatory support for low cardiac output, major bleeding requiring intervention, or vascular complications requiring intervention. Along with early deaths, this information may be important for future patients with iLVSD who are deciding whether to undergo PCI or CABG. These early events may also be used by governance committees to establish whether there are any clinical differences in the number of these events versus expected event rates in normal practice. For this reason, we propose to collect the following SAEs occurring within 30 days of the date of surgery or the date of the first index PCI procedure, for review by governance committees.

1. Stroke
2. New onset end-stage renal failure defined as requiring dialysis
3. Unplanned mechanical circulatory support (IABP, Impella, VA ECMO)
4. Major bleeding requiring reoperation or re-hospitalisation
5. Major vascular complication requiring interventional radiology or surgical intervention
6. All-cause mortality

1.34 SAE REPORTING / CLINICAL OUTCOMES

The main SAEs of interest in the trial are the primary and key secondary outcomes, which are study endpoints, and will be collected via routine data collection after LPLV. These outcomes will be determined as part of the trial analysis. In addition, to assess short term risks, the prespecified list of SAEs within 30 days will be added to the eCRF in a timely fashion (expected within one week) and the data from all centres will be made available 12 monthly (or more frequently if requested) to the DMC, unblinded to the treatment allocation. The investigators believe that the DMC will therefore be best placed to advise the Trial Steering Committee (TSC) and Sponsor as to the safety of participants in the trial and whether any further data should be collected or additional analyses undertaken.

DATA PROTECTION AND PATIENT CONFIDENTIALITY

The LCTU will be the Data Co-ordinating Centre and Data Controller for the BCIS4 trial (UK arm of the STICH-3 Consortium). All data handling and record keeping will be kept in adherence to University of Leicester's (UoL) and NHS Organisation(s) policies. The SWEDEHEART team, Sahlgrenska University Hospital Sweden, will act as the Data Controller for the STICH-3 data worldwide and Data Processor for the STICH-3 Consortium inclusive of UK data.

[figure not shown]
1.35 QUALITY ASSURANCE

Data quality will be optimised through several established strategies. The LCTU has trained and certified study personnel who monitor data quality and follow the necessary Standard Operating Procedures (SOPs). There will be periodic internal database quality-control checks performed, and data audits will be performed during and at the conclusion of the trial.

Numerous checks for consistency of data, including range and limit checks, checks for missing data, and logical consistency checks will be implemented in the ResearchApp™ (Healthbit®) electronic data management software and performed automatically at the time of data entry. Discrepant or inconsistent data will be flagged immediately, queries generated, and the site can respond promptly with corrections while the participant records are immediately available. This is viewable by a 'support dashboard' at both a site and trial management level. Where participants are completing responses to questionnaires via ResearchApp™ (Healthbit®) research staff will be able to manage missing data and incorrect data via this dashboard. Research staff will also be able to send broadcast messages (via push notifications) to remind participants that their follow-up is due. Trial management staff will also be able to view the 'support dashboard' to manage data queries directly with research staff and for where research staff are entering follow-up data on behalf of participants. After a data analysis set has been created from the data collected on the eCRF for analysis, data are further cross-checked, with discrepant observations being flagged and appropriately resolved through a data query system.

There are other processes in place to assure that timely, complete, and high-quality data are obtained. Prior to the start of enrolment, site staff (e.g., investigators, study coordinators) will undergo thorough training regarding the clinical protocol and all data collection procedures, including how to use the ResearchApp™ (Healthbit®) and complete the eCRF data, which will be part of the Site Initiation Visit (SIV). Initial training will occur in an investigators' / coordinators' training virtual meeting with hands-on database interaction. Follow-up additional sessions will be conducted as needed or requested.

